6.5 Database Retention and Archiving of Study Documents

The investigator must retain all study records and source documents for the maximum period required by applicable regulations and guidelines, or institution procedures, or for the period specified by the sponsor, whichever is longer. The investigator must contact BMS prior to destroying any records associated with the study. Location of database and supporting documentation will be outlined in the final observational study report.

All study data (unidentifiable patient data) with supporting documents will be retained by EPID Research for a minimum of 5 years after the publication of results. Secure archives will be maintained for the orderly storage and retrieval of all study related material. An index shall be prepared to identify the archived contents to identify their location. Access to the archives will be controlled and limited to authorized personnel only.

6.6 Registration of Study on Public Website

The study will be registered on the ENCePP’s E-register. The results will also be published on the same site (<http://www.encepp.eu/encepp/studiesDatabase.jsp>). According to the ENCePP Code of Conduct, the principal investigator is responsible of publication of the results.

7 ADVERSE EVENT REPORTING

This study does not meet the criteria for adverse event reporting.

8 GLOSSARY OF TERMS AND LIST OF ABBREVIATIONS

8.1 Glossary of Terms

Not Applicable

8.2 List of Abbreviations

Term	Definition
AF	Atrial fibrillation
ATC	Anatomical Therapeutic Chemical classification
CI	Confidence interval
DDD	Defined daily dose
ENCePP	European Network of Centers for Pharmacoepidemiology and Pharmacovigilance
ID	Personal identification number
HR	Hazard ratio
HUS	Hospital District of Helsinki and Uusimaa
ICD-10	International Classification of Diseases version 10
INR	International Normalized Ratio
Kela	The Social Insurance Institution of Finland
NOAC	New oral anticoagulant
SAP	Statistical analysis plan
SFINX	Swedish, Finnish, INteraction X-referencing
SID	Study identification number
TTR	Time in therapeutic range
VKA	Vitamin K antagonist

APPENDIX 2 ICT NUMBERS AND REFERENCE VALUES FOR LABORATORY PARAMETERS

The ICT numbers for the laboratory variables with the reference values valid in adults in Finland in 2013

Test name	Test abbreviation	ICT number (HUS)		Lower target	Upper target	Unit
International Normalized Ratio	P-INR	4520		2.0	3.0	
Blood picture	B-PVKT	2474				
	B-PVK+TKD	2475				
	B-PVK+Ne	8370				
Hemoglobin	B-Hb	1552	women	117	155	g/L
			men	134	167	g/L
Hematocrit	B-HCT		women	35	46	%
			men	39	50	%
Leukocyte count	fB-Leuk			3.4	8.2	E9/L
erythrocyte count	B-Eryt		women	3.90	5.20	E12/L
			men	4.25	5.70	E12/L
mean corpuscular haemoglobin	E-MCH			27	33	pg/cell
mean corpuscular volume	E-MCV			82	98	fL
platelet count	B-Trom			150	360	E9/L
Creatinine	P-Crea	4600	women	50	90	μmol/L
			men	60	100	μmol/L
Alanine aminotransferase	P-ALAT	1024	women	10	45	U/L
			men	10	70	U/L

Source: Laboratory of Helsinki University Central Hospital. Available at: http://huslab.fi/cgi-bin/ohjekirja/tt_show.exe?assay=2475&terms=pvk. Accessed February 25, 2013.

Note: The ICT numbers may not be the ones mentioned above if the laboratory is using some data system other than Hospital District of Helsinki and Uusimaa (HUS).

APPENDIX 3 ATCS INCLUDED IN THE STUDY

Possible changes in the ATC code during the study period are taken into account by Kela – The Social Insurance Institution of Finland.

B01AA03: warfarin

Antiarrhythmics:

Group C01B: antiarrhythmics, classes I and III (listed in detail in Table 1)

Group C07: beta blockers / class II antiarrhythmics (listed detail in [Table 2](#))

C08DB01: diltiazem (class IV antiarrhythmic)

C08DA01: verapamil (class IV antiarrhythmic)

C01EB10: adenosine (other type antiarrhythmic)

Table 1: C01B ANTIARRHYTHMICS, CLASS I AND III

C01BA Antiarrhythmics, class Ia	
C01BA01	quinidine
C01BA02	procainamide
C01BA03	disopyramide
C01BA04	sparteine
C01BA05	ajmaline
C01BA08	prajmaline
C01BA12	lorajmine
C01BA51	quinidine, combinations excl. psycholeptics
C01BA71	quinidine, combinations with psycholeptics
C01BB Antiarrhythmics, class Ib	
C01BB01	lidocaine
C01BB02	mexiletine
C01BB03	tocainide
C01BB04	aprindine
C01BC Antiarrhythmics, class Ic	
C01BC03	propafenone
C01BC04	flecainide
C01BC07	lorcainide
C01BC08	encainide
C01BD Antiarrhythmics, class III	
C01BD01	amiodarone
C01BD02	bretylum tosilate
C01BD03	bunaftine
C01BD04	dofetilide
C01BD05	ibutilide
C01BD06	tedisamil
C01BD07	dronedarone
C01BG Other antiarrhythmics, class I and III	
C01BG01	moracizine
C01BG07	cibenzoline
C01BG11	vernakalant

Table 2: C07A BETA BLOCKING AGENTS

C07AA Beta blocking agents, non-selective	
C07AA01	alprenolol
C07AA02	oxprenolol
C07AA03	pindolol
C07AA05	propranolol
C07AA06	timolol
C07AA07	sotalol
C07AA12	nadolol
C07AA14	mepindolol
C07AA15	carteolol
C07AA16	tertatolol
C07AA17	bopindolol
C07AA19	bupranolol
C07AA23	penbutolol
C07AA27	cloranolol
C07AA57	sotalol, combinations
C07AB Beta blocking agents, selective	
C07AB01	practolol
C07AB02	metoprolol
C07AB03	atenolol
C07AB04	acebutolol
C07AB05	betaxolol
C07AB06	bevantolol
C07AB07	bisoprolol
C07AB08	celiprolol
C07AB09	esmolol
C07AB10	epanolol
C07AB11	s-atenolol
C07AB12	nebivolol
C07AB13	talinolol
C07AB52	metoprolol, combinations
C07AB57	bisoprolol, combinations
C07AG Alpha and beta blocking agents	
C07AG01	labetalol
C07AG02	carvedilol
C07B BETA BLOCKING AGENTS AND THIAZIDES	
C07BA Beta blocking agents, non-selective, and thiazides	
C07BA02	oxprenolol and thiazides
C07BA05	propranolol and thiazides
C07BA06	timolol and thiazides
C07BA07	sotalol and thiazides
C07BA12	nadolol and thiazides
C07BA68	metipranolol and thiazides, combinations
C07BB Beta blocking agents, selective, and thiazides	
C07BB02	metoprolol and thiazides
C07BB03	atenolol and thiazides
C07BB04	acebutolol and thiazides
C07BB06	bevantolol and thiazides
C07BB07	bisoprolol and thiazides
C07BB12	nebivolol and thiazides
C07BB52	metoprolol and thiazides, combinations
CC07BG Alpha and beta blocking agents and thiazides	
C07BG01	labetalol and thiazides

Table 2: C07A BETA BLOCKING AGENTS

C07AA Beta blocking agents, non-selective

C07C BETA BLOCKING AGENTS AND OTHER DIURETICS

C07CA Beta blocking agents, non-selective, and other diuretics

C07CA02 oxprenolol and other diuretics

C07CA03 pindolol and other diuretics

C07CA17 bopindolol and other diuretics

C07CA23 penbutolol and other diuretics

C07CB Beta blocking agents, selective, and other diuretics

C07CB02 metoprolol and other diuretics

C07CB03 atenolol and other diuretics

C07CB53 atenolol and other diuretics, combinations

C07CB Beta blocking agents, selective, and other diuretics

C07CB02 metoprolol and other diuretics

C07CB03 atenolol and other diuretics

C07CB53 atenolol and other diuretics, combinations

C07CG Alpha and beta blocking agents and other diuretics

C07CG01 labetalol and other diuretics

C07D BETA BLOCKING AGENTS, THIAZIDES AND OTHER DIURETICS

C07DA Beta blocking agents, non-selective, thiazides and other diuretics

C07DA06 timolol, thiazides and other diuretics

C07DB Beta blocking agents, selective, thiazides and other diuretics

C07DB01 atenolol, thiazides and other diuretics

C07E BETA BLOCKING AGENTS AND VASODILATORS

C07EA Beta blocking agents, non-selective, and vasodilators

C07EB Beta blocking agents, selective, and vasodilators

C07F BETA BLOCKING AGENTS AND OTHER ANTIHYPERTENSIVES

C07FA Beta blocking agents, non-selective, and other antihypertensives

C07FA05 propranolol and other antihypertensives

C07FB Beta blocking agents, selective, and other antihypertensives

C07FB02 metoprolol and other antihypertensives

C07FB03 atenolol and other antihypertensives

C07FB07 bisoprolol and other antihypertensives

Source: WHO Collaborating Centre for Drug Statistics Methodology. ATC/DDD Index. December 2012. Available at: http://www.whocc.no/atc_ddd_index/?code=C&showdescription=yes.

Class D interactive drugs according to SFINX

Excluding etofenamate with topical ATC only; ATCs only for systemic exposure with an exception of econazole are listed in Table 3.

Table 3: Class D interactive drugs according to SFINX**Drugs increasing bleeding risk without affecting warfarin exposure or INR**

ticlopidine	B01AC05		
NSAIDs:			
dexibuprofen	M01AE14		
dexketoprofen	M01AE17		
diclofenac	M01AB05	M01AB55	
etodolac	M01AB08		
flurbiprofen	M01AE09		
ibuprofen	M01AE01	M01AE51	C01EB16
indometacin	M01AB01	M01AB51	C01EB03
ketoprofen	M01AE03	M01AE53	
ketorolac	M01AB15		
lornoxicam	M01AC05		
meclofenamic acid	M01AG04		
mefenamic acid	M01AG01		
meloxicam	M01AC06	M01AC56	
nabumetone	M01AX01		
naprokseeni	M01AE02	M01AE52	M01AE56
niflumic acid	M01AX02		
niesulide	M01AX17		
phenylbutazone	M01AA01	M01BA01	
piroxicam	M01AC01		
sulindac	M01AB02		
tenoxicam	M01AC02		
tiaprofenic acid	M01AE11		
tolfenamic acid	M01AG02		
Coxibs:			
celecoxib	M01AH01	L01XX33	
etoricoxib	M01AH05		
lumiracoxib	M01AH06		
rofecoxib	M01AH02		
parecoxib	M01AH04		
valdecoxib	M01AH03		

Other analgetics:

Table 3: Class D interactive drugs according to SFINX

acetylsalicylic acid	B01AC06	M01BA03	N02BA01	N02BA51	N02BA71
diflunisal	N02BA11				

Drugs raising bleeding risk by increasing warfarin exposure (and INR):

Antifungals:

ekonatsoli	D01AC03	G01AF05				
fluconazole	J02AC01					
metronidazole	A02BD01	A02BD02	A02BD03	A02BD08	J01XD01	P01AB01
miconazole	A07AC01	J02AB01				
sulfamethoxazole	J01EC01	J01EE01				

Miscellaneous:

cimetidine	A02BA01	A02BA51			
clofibrate	C10AB01	C10AB03			
fluvoxamine	N06AB08				
noscapine	R05DA07				
silymarin	A05BA03				
tramadol	N02AX02	N02AX52			

Drugs increasing the risk of embolism by decreasing warfarin exposure (and INR):

colestyramine	C10AC01
mitotane	L01XX23

ATC=Anatomical Therapeutic Chemical; INR=international normalized ratio; NSAIDs=non-steroidal anti-inflammatory drugs.

Source: 1.) SFINX Drug database. Class D interactive drugs. Accessed February 18, 2013. Available at: http://www.medbase.fi/sfinx/whatis_finx.htm. and 2.) WHO Collaborating Centre for Drug Statistics Methodology. ATC/DDD Index. December 2012. Available at: http://www.whocc.no/atc_ddd_index.

APPENDIX 4 COMORBIDITIES

Variable	Definition (ICD-10)
Hypertension	I10-I15
Thyreotoxicosis	E05
Cardiomyopathy	I420-I422, I429
Congestive heart failure	I50
Diabetes	E10-E14
Stroke	I63, I64, I693-I698
Transient ischemic attack*	G45
Vascular disease	I20-I25, I65-I66, I672, I70
Cancer	C00-C97, D00-D09
Pulmonary embolism	I26
Other venous thromboembolism	I80-183

ICD=International Statistical Classification of Diseases and Related Health Problems.

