3 STUDY DESIGN

3.1 Overview of Study Design

The study with cohort design is conducted as a nationwide retrospective register-based linkage study using data obtained from the Finnish health care registers. The study population consists of all AF patients using warfarin with INR measurements in selected hospital district areas in Finland between 01-Jan-2007 and 3-Dec-2009.

Index date: Index date is defined as the date of first purchase of warfarin after 01-Jan-2007.

Follow-up period: Follow-up of the patients starts on the index date, and ends on 31-Dec-2011, at time of death or at time of emigration whichever occurs first.

History period: Treatment and comorbidity history is gathered from the period 01-Jan-2005 through 31-Dec-2006.

The key milestones of the study process are given below (Table 3.1-1). Note that the timelines are estimates only and are subject to change depending on the duration of the data permission processes and actual receipt of the data from the register holders.

Table 3.1-1: Study Timelines

Milestone	Anticipated date
Study protocol approved	4-Mar-2013
Registration in the ENCePP e-Register	30-Apr-2013
Ethics committee approval	30-Apr-2013
Data permit approvals	30-Jun-2013
Receipt of data from register holders	30-Sep-2013
Final study report	30-Dec-2013

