3.3 Data Source/Data Collection Process

The study timelines are presented in the picture below:

Figure 3.3-1: Study Timelines

[figure not shown]

Table 3.3-1: Study Registers

Register	Register Holder	Information obtained
National Prescription Register	Kela – The Social Insurance Institution of Finland	Drug purchases (ATC codes)
National Reimbursement Register	Kela	Reimbursement decisions 207 for chronic arrhythmias (for population characterization)
Finnish Care Register, HILMO	National Institute for Health and Welfare	Diagnoses (ICD10 codes) and date of diagnosis
National Causes of Death Register	Statistics Finland	Time of death and causes of death (ICD-10 codes)
Laboratory databases	HUSLAB + other hospital laboratories	INR measurements and other relevant laboratory values
Finnish Cancer Registry	National Institute for Health and Welfare	Cancer diagnosis (ICD-O-3 codes) and date of diagnosis
Population Register	Population Register Center	Places of domicile 12 months prior to and on index dates.
Social HILMO	National Institute for Health and Welfare	Information (dates) about institutionalization (other than hospitalization)

- Data will be requested from the registry holders ([Table 3.3-1](#)) based on the study protocol.
- Data permits will be requested from each registry holder based on the study protocol and ethical approval.
- Approval of Ethical Review Board of Hospital District of Helsinki and Uusimaa (HUS) will be requested to cover the nationwide study.
- This is a fully register-based study and patients will not be contacted in any phase of the study.
- Warfarin exposure will be defined by Kela, who then will convert the patient IDs to study IDs (SIDs). Kela will then send the IDs and the SIDs to other register holders: Statistics Finland, National Institute for Health and Welfare, Statistics Finland, Population Register Center, and central hospital laboratories included in the study.
- EPID Research will receive unidentifiable data including SIDs only. All patient data handled by the researchers are then anonymous which ensures full data protection of the patients.

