3.4.3 Other Covariates/Control Variables

- Reimbursement code 207
 - Yes/no
- Information about hospitalizations and institutionalization (other than hospitalization)

- dates
- will be taken into account when defining the discontinuation of warfarin treatment
- Laboratory parameters for anemia characterizations
 - Blood picture
 - ◆ Haemoglobin
 - decrement of 20 g/L
 - being under the reference value
 - See [Appendix 2](#) for details.
- Concomitant use of class D interactive drugs according to SFINX (Swedish, Finnish, INteraction X-referencing, see [Appendix 3, Table 3](#) for complete ATC listing)
 - Concomitant use during the warfarin treatment period assumed by the purchases and exposure (see definition for exposure in Section 4.1).
- Age*
- Gender*
- Hospital district
 - Helsinki, Turku, Tampere, Kuopio, Oulu, Jyväskylä
 - other possible central hospitals
- CHADS₂^{11 12}
- CHA₂DS₂-VASc^{11,12}
- Comorbidities (more in detail in [Appendix 4](#))
 - Hypertension*
 - Thyrotoxicosis
 - Cardiomyopathy
 - Congestive heart failure*
 - Diabetes*
 - Stroke*
 - Transient ischemic attack*
 - Vascular disease**
 - Cancer
 - Venous thromboembolism
 - *included in CHADS₂ score and in CHA₂DS₂-VASc score
 - **included in CHA₂DS₂-VASc score.

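### Heart failure is defined by I50 alone, so patients recorded only under I110, I130 or I132 count as hypertensive but not as having heart failure (minor)

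*Protocol*

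**What the plan says.** Protocol Section 3.4.3 lists the comorbidities used as covariates and sends the reader to the code list ("more in detail in [Appendix 4"). It stars both hypertension and "Congestive heart failure", and explains the star as "included in CHADS₂ score and in CHA₂DS₂-VASc score". No separate code list is given for the two scores, so the Appendix 4 definitions feed them.

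Appendix 4 defines heart failure by "Congestive heart failure I50" and hypertension by "Hypertension I10-I15". The list goes to four characters where its authors wanted that, as in "Cardiomyopathy I420-I422, I429". No rule says that one code may count under two conditions.

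The diagnoses come from the Finnish Care Register ("Diagnoses (ICD10 codes) and date of diagnosis", Table 3.3-1). The window for prior disease is fixed in Section 3.1: "Treatment and comorbidity history is gathered from the period 01-Jan-2005 through 31-Dec-2006".

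These variables are used in three places:
- Section 4.1.1 stratifies the incidence rates by the other covariates.
- The same section adjusts the Cox models for them.
- Section 4.1.3, Objective 7, tabulates warfarin users by comorbidity.

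**The concern.** ICD-10 does not place every heart-failure diagnosis under I50. Hypertensive heart disease with heart failure is I110, and hypertensive heart and renal disease with heart failure is I130 or I132. Under Appendix 4 these codes set the hypertension indicator and leave the heart-failure indicator at zero. The diagnosis is in the data, but the code list credits it to one condition only.

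The error runs in one direction: heart failure is under-counted and never over-counted by this route. It affects three things:
- Both risk scores are too low for these patients.
- The group without heart failure, in the stratified rates and the models, contains some patients who have it.
- Heart failure is under-reported in the comorbidity table, which is itself a planned result.

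If heart failure is related both to INR control and to outcome, some confounding would also remain in the adjusted INR hazard ratios.

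**Working it through.** The plan states no figure on this point, so there is none to reproduce. The check is a test of the code lists, followed by illustrative sizes.

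**1. Where each code falls in Appendix 4**

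| Code | Hypertension (I10-I15) | Heart failure (I50) | Cardiomyopathy (I420-I422, I429) | Vascular disease (I20-I25, I65-I66, I672, I70) |
|---|---|---|---|---|
| I110 | yes | no | no | no |
| I130 | yes | no | no | no |
| I132 | yes | no | no | no |
| I500 | no | yes | no | no |

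**2. Who is affected**

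- I50 in the history period, with or without one of the three codes: heart failure = yes, scored correctly.
- I110, I130 or I132 in the history period and no I50: hypertension = yes, heart failure = no. The hypertension point is kept and the heart-failure point is lost. Each score is one too low, taking heart failure as one point in each score. The protocol marks it as a component but does not print the weights.

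**3. How many**

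Input from Section 4.2: study population 32 000. Assumed, because the documents give neither: heart-failure prevalence p = 10-30%, and share s = 1-10% of those patients coded only under the three codes. Affected = 32 000 × p × s.

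- Low end: 32 000 × 0.10 × 0.01 = 32 (0.1%).
- Middle: 32 000 × 0.20 × 0.05 = 320 (1.0%).
- High end: 32 000 × 0.30 × 0.10 = 960 (3.0%).

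At the high end a true prevalence of 30% would be tabulated as 30% − 3% = 27%. At the low end 10% would appear as 10% − 0.1% = 9.9%.

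**4. Possible bias in an INR hazard ratio**

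This is an illustration with every input assumed: heart failure in 35% of low-INR time and 25% of reference time, a mortality hazard ratio of 2 for heart failure, and a share s missed in both groups. Among those recorded as free of heart failure, the fraction who have it is f = p·s / (1 − p + p·s). Their mean hazard, relative to patients truly free of it, is 1 + f.

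- s = 3%: low INR f = 0.0105 / 0.6605 = 0.0159; reference f = 0.0075 / 0.7575 = 0.0099. Ratio 1.0159 / 1.0099 = 1.006, a bias of 0.6%.
- s = 10%: low INR f = 0.035 / 0.685 = 0.0511; reference f = 0.025 / 0.775 = 0.0323. Ratio 1.0511 / 1.0323 = 1.018, a bias of 1.8%.

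The stratum recorded as having heart failure has no error from this source, so the estimate pooled over both strata is biased by less than these figures. For comparison, the smallest difference that Section 4.2 claims to detect with about 80% power or more is 10%, at 6 events per 100 person-years.

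**The case against.** The strongest objection is that the protocol never names I110, I130 or I132 and does not say what they mean, so the point draws on something outside the documents. That is true of the labels. But ICD-10 is the protocol's own coding language for inclusion, outcomes and comorbidities, and a code list can be checked only by reading its codes against that classification. This does not depend on recalling a result from a cited study.

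A second objection is that nothing in the protocol is contradicted. I50 for heart failure and I10-I15 for hypertension are compatible, and the references cited for the scores are not available to show a departure. This stands: the fault is a narrow code list, not an internal inconsistency. The list is nevertheless fixed in the protocol and not left to the SAP, and followed as written it misclassifies the patients described.

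Third, the size rests wholly on assumptions. The range of 32 to 960 patients is thirty-fold, and the documents do not say how often the register uses these codes or whether I50 is recorded beside them. The documents also give no source for a link between heart failure and unstable INR. All of this stands and keeps the point minor. The two-year history period limits the chance that a separate I50 record is captured, but by how much cannot be said.

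Two stronger readings are tempting. A reader might infer that patients with a registered heart-failure code in general score zero for heart failure. They do not: anyone with an I50 record in the history period is scored correctly. A reader might also infer that the INR hazard ratios, especially for mortality, are materially confounded. Nothing in the documents supports that, and the illustration puts the bias at 1.8% or less. The affected patients also remain adjusted through the hypertension covariate and are one point off on the scores, not unadjusted.

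**Conclusion.** The point holds as a minor defect in a covariate definition. Patients with I110, I130 or I132 and no I50 record in the history period are credited with hypertension but not heart failure. They score one point too low on both scores, sit in the wrong heart-failure stratum and are missing from the heart-failure row of the comorbidity table.

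The code assignment follows directly from Appendix 4 and Section 3.4.3, read with the ICD-10 labels. The number affected cannot be derived from the documents; 0.1-3.0% of the cohort is the range under the assumptions shown. The effect on the INR hazard ratios is probably small. Exposure, endpoints, reference category and power calculation are untouched.

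**What to change.** In Appendix 4, define congestive heart failure as I50, I110, I130, I132. Keep hypertension at I10-I15, and add a note that the three codes count for both conditions. If leaving them out was deliberate, state the reason there instead.

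The cost is one line in the code list. The codes already lie in the range to be extracted for hypertension, so no new data are needed.
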